7.3.2 Power for Behavioral Endpoints

One third of the networks will be enrolled in Philadelphia, approximately 150 networks per arm; the remainder will be enrolled in Thailand, approximately 300 per arm. Due to the lower seroincidence in the Philadelphia site, it will not be possible to assess the effect of the intervention at that site using primary outcome information. Differences in secondary outcomes of self-reported behavioral outcomes will be assessed to evaluate the intervention at the Philadelphia site (as well as in Thailand).

For behavioral endpoints, assuming repeated measurement at each visit and a conservative average of 12 visits per network [average number of visits per participant = 5, average number of members = 2.9, loss to follow-up/year = 10%], the formula above can be used to estimate the power for change of behavior within the networks. P_{Exp} and $P_{Control}$ are the

probabilities of a behavior in the previous six-month period. As shown in Table 2 below, there is adequate power to detect 10% behavioral change among networks at the Philadelphia site, depending upon the prevalence in the control arm and the correlation within networks.

			Networks/arm				
P_{Exp}	$P_{Control}$	К	Power: 80%	Power: 90%			
40	50	0.1	68	91			
		0.2	103	138			
		0.3	138	185			
30	40	0.1	62	83			
		0.2	95	127			
		0.3	127	170			
20	30	0.1	51	69			
		0.2	78	104			
		0.3	105	140			
10	20	0.1	35	46			
		0.2	53	71			
		0.3	71	95			

 Table 2: For network aggregates: Sample size requirements for testing proportions with repeated measurements: cluster size=12

Similarly, for testing behavioral change amongst the network indexes, sample size estimates have been computed for repeated measures from the five visits of the index participant. Table 3 shows adequate power at the Philadelphia site for detecting 15% behavioral change in the networks depending on the correlation within networks and the prevalence in the control arm.

			Networks/arm	
P Experimental	P Control	К	Power: 80%	Power: 90%
35	50	0.1	47	63
		0.2	60	81
		0.3	74	99
25	40	0.1	42	56
		0.2	54	72
		0.3	66	88
15	30	0.1	24	45
		0.2	33	57
		0.3	43	70
10	20	0.1	55	74
		0.2	71	95
		0.3	87	116

 Table 3: For network indexes: Sample size requirements for testing proportions with repeated measurements: cluster size=5

There is close to 90% power for detecting 10% change in behavior in the networks' aggregates in the Philadelphia. There is close to 90% power for detecting 15% behavior change in the network indexes at the Philadelphia site.

7.3.3 Power for Assessment of Intervention Effect on Behavior

In the event of a successful trial outcome based on the primary endpoint, an analysis of behavioral correlates addresses the question of whether the behavioral changes observed at both sites make it plausible that the intervention is effective in both sites, Thailand and Philadelphia. This analysis has two distinct stages. During the first stage, behaviors that are most important mediators of the intervention effect on HIV seroincidence will be established. Explicitly, these are behavioral measures that, when added to the model of the effect of the intervention on seroincidence, 1) have significant coefficients in the expected direction and 2) substantially reduce the size of the intervention effect. They are thus correlated with seroincidence and substantially account for the observed intervention effect. This argues the plausibility of a behavior being a partial surrogate of the treatment effect.^{33,34,35} Behaviors meeting these criteria will then be used in the second stage of the analysis, which would examine whether the difference in behavior change observed between the intervention and control arms is preserved in the two sites. Power calculations are only provided for the simplest case of a dichotomous outcome, where the analysis reduces to a 2x2 table of behavior proportions by site and arm. The null hypothesis states that the relative behavior change at each site is the same. Under the alternative, the behavior change between arms is different at the sites; formally, the test boils down to a test for a non-zero interaction term.

Presented in Table 4 below are the 80% power boundary probabilities for the given sample size of the trial, expressed as cell probabilities. Power computations are based on use of generalized linear models for binomial data. For these calculations, the sample size is taken as fixed by the requirement for adequate power for the primary endpoint, at 445 networks of average size 2.9 per arm, and it is assumed 2/3 of the networks are in Thailand.

It is expected that the probabilities for behavioral endpoints will be in the range of 20-80%, so power computations are over this range. The upper bound is the probability for the intervention arm at the Philadelphia site that, if it were true, there would be 80% probability of detecting it was not the same behavior reduction as seen in Thailand. For example, in the first row of the table below, it is assumed that a behavior has 80% prevalence in the control arm in both the Philadelphia and Thailand sites at the conclusion of the trial. It is assumed that, in the intervention arm in Thailand, the prevalence of this behavior is halved to 40%. The null hypothesis is that the same is true in Philadelphia. If the true prevalence in Philadelphia were 62% or 26%, there would be 80% power to detect this. Three scenarios are considered in Table 4: prevalence is the same in Philadelphia and Thailand; prevalence is lower, and prevalence is higher in Philadelphia.

Scenario	Thailand,	Philadelphia,	Thailand,	Philadelphia, Intervention			
	p_{00}	p_{01}	Intervention p_{10}	Null p_{11}	Lower Bound	Upper Bound	
Equal site	0.8	0.800	0.40	0.400	0.258	0.619	
prevalence	0.5	0.500	0.25	0.250	0.156	0.401	
	0.2	0.200	0.10	0.100	0.056	0.178	
Lower	0.8	0.600	0.40	0.300	0.191	0.471	
Philadelphia	0.5	0.375	0.25	0.188	0.115	0.307	
Prevalence	0.2	0.150	0.10	0.075	0.041	0.136	
Higher	0.8	0.850	0.40	0.425	0.275	0.656	
Philadelphia	0.5	0.625	0.25	0.312	0.197	0.496	
Prevalence	0.2	0.250	0.10	0.125	0.118	0.338	

 Table 4: Analysis of behavioral correlates: bounds on probabilities for which the trial has 80%
 power to detect differences in behavior change in Philadelphia vs. Thailand.

The alternatives that there is reasonable power to detect seem useful; that is, they represent clinically relevant differences that are neither too small nor too broad.

There are necessarily several points of scientific, rather than statistical, interpretation in the analysis of behavioral correlates. In the first stage of the analysis, there is a judgment of whether a behavioral measure is a substantial mediator of intervention effect. Given the multifaceted nature of behavior change, no single behavioral measure would be expected to fully capture any observed treatment effect.

In the second stage, power calculations are presented for a single dichotomous behavioral outcome per participant. The trial will collect repeated measure data, so there is a risk the study will ultimately be overpowered to detect interaction effects. That is, the intervention effects within each site may be different using a statistical metric, but clinically those differences may not be relevant. An alternate approach would be to establish a clinically relevant difference and reject behavioral changes as the same using an objective standard.

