7.3 Sample Size and Accrual

Sample size estimates are based on a group, randomized design, where all members of a network are randomized to the same arm. The sample size required with a group-randomized design is increased depending on the strength of correlation between outcomes within a network, relative to an individually randomized design.

Sample size computations use the formulation given by Donner et al^{32} , where the total number of participants per arm required in a design with clusters of size *n* is given as:

$$T = \frac{(Z_{\alpha} + Z_{\beta})^{2} (P_{E}(1 - P_{E}) + P_{C}(1 - P_{C}))(1 + (n - 1)\kappa)}{(P_{E} - P_{C})^{2}}$$

where Z_{α} , Z_{β} are standardized Normal quantiles for type I error α and power $1 - \beta$, P_E and P_C are, respectively, the cumulative probability of seroconversion in the experimental and control arms, and κ is analogous to an intraclass correlation coefficient. The number of networks required per arm is then $\frac{T}{n}$.

 κ can be expressed as:

$$\kappa = \frac{P_1^* + P_0^* - (P^n + (1 - P)^n)}{1 - (P^n + (1 - P)^n)}$$

where P_1^* and P_0^* are the probabilities of network concordance, i.e. the probability all and none of the members of network seroconvert, respectively. The numerator of κ measures the difference between the actual concordance among clusters and the expected concordance rate under the assumption of independence, i.e. κ measures how much agreement exists in a cluster beyond the amount expected by chance.

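### Protocol 7.3.3: the Table 4 bounds labelled as 80% power points do not follow from any single sample size, and the last row contradicts its own null

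*Protocol*

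**What the plan says.** Section 7.3.3 covers the test of whether the intervention's effect on a mediating behavior is the same in Thailand and Philadelphia (secondary objective 4). It fixes the calculation as follows.

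- Size: "at 445 networks of average size 2.9 per arm, and it is assumed 2/3 of the networks are in Thailand".
- Model: "Power computations are based on use of generalized linear models for binomial data".
- Null: "The null hypothesis states that the relative behavior change at each site is the same".
- Unit: "power calculations are presented for a single dichotomous behavioral outcome per participant".
- Claim for the table: "Presented in Table 4 below are the 80% power boundary probabilities for the given sample size of the trial, expressed as cell probabilities".
- Worked example, from the first row (control 80% at both sites, Thailand intervention 40%): "If the true prevalence in Philadelphia were 62% or 26%, there would be 80% power to detect this".

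The section states no alpha, within-network correlation or loss to follow-up for Table 4. Elsewhere, section 7.3 says: "The sample size required with a group-randomized design is increased depending on the strength of correlation between outcomes within a network". Tables 1 to 3 carry kappa from 0.1 to 0.3. The primary-endpoint calculation in 7.3.1 uses two-sided alpha 0.05, kappa 0.2 and 10% loss per year. After Table 4, the protocol judges the detectable differences to be useful and of sensible size.

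**The concern.** If every bound were an 80% power point for the same four cells and the same sample, solving each row for its sample size would return about 1,290 per arm throughout. It does not, and the discrepancies run in both directions.

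Table 4 is the protocol's only power statement for the cross-site comparison. Section 2.3 relies on that comparison to argue that the intervention works in different settings, because 7.3.2 says Philadelphia cannot be judged on the primary outcome. A reader using the table would expect a common behavior to show an interaction only for large site differences, when much smaller ones would be detected. For a behavior at 20% prevalence, the same reader would take a non-significant interaction as stronger evidence of similarity than the printed power warrants.

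**Working it through.** **Inputs.** N per arm = 445 × 2.9 = 1,290 (7.3.3), two thirds in Thailand. Alpha is taken as two-sided 0.05, carried over from 7.3.1 as an assumption. Cells: p00 and p10 are Thailand control and intervention; p01 and p11 are Philadelphia control and intervention. Rows are counted from the top of Table 4.

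**What reproduces.** Every printed null equals p01 × p10 / p00 (row 4: 0.6 × 0.4 / 0.8 = 0.300), so the scale is relative change, that is, a log link. In rows 1 to 8 the bounds are symmetric about the null on that scale (row 1: √(0.258 × 0.619) = 0.400).

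**Formulas.** V = 1.5(1−p00)/p00 + 3(1−p01)/p01 + 1.5(1−p10)/p10 + 3(1−p11)/p11. SE² = V × DE / N. Power = Φ(|ln(p11/null)|/SE − 1.96). Solving for 80% power with DE = 1 gives N = (1.96 + 0.842)² × V / ln(p11/null)², where the squared term is 7.85.

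**Implied N, variance at the null.**
- Row 1: V = 0.375 + 0.75 + 2.25 + 4.5 = 7.875; ln(0.258/0.400)² = 0.192; N ≈ 321.
- Row 6: V = 6 + 17 + 13.5 + 37 = 73.5; ln(0.041/0.075)² = 0.365; N ≈ 1,582.

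**Power, independent participants, variance at the alternative.**
- Row 1, bound 0.258: V = 12.00, SE = 0.0964, 0.4385/0.0964 = 4.55, power 99.5%.
- Row 6, bound 0.041: V = 106.7, SE = 0.2875, 0.6039/0.2875 = 2.10, power 56%.

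Power ranges below span variance at the alternative and at the null.

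| Row (p00/p01) | Bounds | Implied N per arm, lower/upper bound | Power at N = 1,290, independent |
|---|---|---|---|
| 1 (0.8/0.8) | 0.258, 0.619 | 321/324 | >99%, >99% |
| 2 (0.5/0.5) | 0.156, 0.401 | 635/633 | 92-98%, 98-99.6% |
| 3 (0.2/0.2) | 0.056, 0.178 | 1,366/1,381 | 63-78%, 77-87% |
| 4 (0.8/0.6) | 0.191, 0.471 | 448/448 | 97-99.7%, >99% |
| 5 (0.5/0.375) | 0.115, 0.307 | 788/775 | 85-95%, 95-99% |
| 6 (0.2/0.15) | 0.041, 0.136 | 1,582/1,629 | 56-72%, 70-82% |
| 7 (0.8/0.85) | 0.275, 0.656 | 299/300 | >99%, >99% |
| 8 (0.5/0.625) | 0.197, 0.496 | 531/530 | 96-99%, >99% |

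The implied N varies more than fivefold. A different alpha, a common design effect or a common loss factor multiplies every row by the same number, so none of them can reconcile the rows.

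**Row 9 (0.2/0.25).** The printed null is 0.25 × 0.10 / 0.20 = 0.125, but √(0.118 × 0.338) = 0.200. At N = 1,290, power is about 5% at 0.118 and over 99% at 0.338.

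**With clustering.** DE = 1 + 1.9κ, which is 1.19, 1.38 and 1.57 for κ = 0.1, 0.2 and 0.3. At κ = 0.2 the effective size is 1,290/1.38 ≈ 935.
- Row 3: 50-64% at 0.056 and 64-75% at 0.178.
- Row 6: 43-58% at 0.041 and 57-69% at 0.136.
- Across κ = 0.1 to 0.3, rows 3 and 6 span about 39-81%.
- The worked example stays at 95% or more throughout.

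**Other link.** A logit interaction at κ = 0.2 gives about 80% at 0.258, but 98% at 0.619 and 38-71% in rows 3 and 6. It also does not match the printed nulls.

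**The case against.** - **Kappa and alpha are borrowed.** Section 7.3.3 gives neither, and kappa 0.2 was chosen for seroconversion. Without clustering, the upper bounds of rows 3 and 6 have 70-87% power, which straddles 80%. At a critical value of 1.645 with null variance and independence, all four bounds in those rows reach 80-86%. This stands as a limit on how firmly the low-prevalence shortfall can be stated. It does not touch the inconsistency between rows, because alpha rescales all of them alike and raises the worked example still further above 80%.
- **The table may carry an undisclosed variance term.** The squared log half-widths of rows 1 to 8 are fitted closely by the binomial sum plus a constant, so the table looks systematic. But the fitted slope implies about 3,000 people per arm, and the protocol describes no such term, so the stated inputs still do not give the printed bounds.
- **Repeated measures.** A reader might infer that the trial itself would miss site differences in uncommon behaviors far more often than one time in five. The documents do not support that. Section 7.3.3 says the table uses one outcome per participant and warns that repeated data may overpower the interaction test; sections 7.5.2 and 7.5.3 plan repeated-measures and behavioral-correlate models. With the 12 visits per network of 7.3.2 (already net of 10% annual loss) and κ = 0.2, effective size is 445 × 12 / (1 + 11 × 0.2) ≈ 1,669 per arm. Power is then 67-82% at 0.041, 81-90% at 0.136, 74-87% at 0.056 and 87-94% at 0.178.
- **Little depends on the table.** The analysis is secondary and conditional on a positive primary result, and the sample size is fixed by the primary endpoint. That limits the weight of the point but does not make the printed power correct.

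**Conclusion.** The point holds as an error in the stated power. Given the stated size, model and null, no single sample size makes the bounds in rows 1 to 8 80% power points: they imply about 300 to 1,630 per arm against 1,290. The worked example is far too wide, with at least 99% power under independence and at least 95% for kappa up to 0.3. The lower bounds of rows 3 and 6 fall short even under independence (63-78% and 56-72%), given two-sided alpha 0.05. The upper bounds of those rows fall clearly short only if clustering is counted, at kappa 0.2 or more. Row 9 is wrong on its face, with no assumption about alpha or kappa needed.

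What does not follow is that the planned repeated-measures analysis is underpowered, or that the trial needs more participants. The finding concerns what Table 4 says about a single dichotomous outcome.

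**What to change.** Recompute all nine rows from one stated effective size, 1,290 × (proportion retained) / (1 + 1.9κ) per arm, for κ = 0.1, 0.2 and 0.3, with alpha and the 10% annual loss made explicit. The worked example defines prevalences at the conclusion of the trial, so loss belongs in the calculation. Over the 27-month average follow-up in 7.3.1, retention is 0.9^2.25 ≈ 79%.

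For illustration, with κ = 0.2, two-sided alpha 0.05 and variance at the alternative:

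| Row | Printed bounds | 80% bounds, no loss | 80% bounds, 79% retained |
|---|---|---|---|
| 1 | 0.258/0.619 | 0.30/0.50 | 0.29/0.52 |
| 3 | 0.056/0.178 | 0.039/0.185 | 0.032/0.198 |
| 6 | 0.041/0.136 | 0.023/0.147 | 0.017/0.158 |
| 9 | 0.118/0.338 | 0.055/0.222 | 0.047/0.236 |

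Replace the worked example with the recomputed first row, and revisit the sentence that calls the detectable differences useful. State that these are single-outcome figures and that the planned repeated-measures analysis may have more power.

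The cost is one recalculated table and a few sentences in 7.3.3, with a less favorable statement for uncommon behaviors. Enrolment, procedures and the primary analysis are unchanged.

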7.3.1 Power for seroincidence endpoints

Philadelphia has established a seroincidence rate of 2 per 100 person-years and the current rate established in Thailand among IDU is 10.4 per 100 person-years, although in the sample size computations a conservative 8% rate is used. One-third of the networks will enroll in Philadelphia and two-thirds in Thailand.

Sample size computations are made using the following assumptions:

- Mean seroincidence rate: 6% per year for pooled sites, 8% per year for the Thai sites.
- Loss to follow up 10% per year
- 30 months recruitment, minimum 18 months follow up, maximum 30 months
- 90% power, 5% Type I error

The formula above is used, substituting for P_E and P_C estimates \overline{P}_E and \overline{P}_C , the average probability of seroconverting during the study on the experimental and control arms. These estimates take loss to follow-up and differential length of follow-up into account.

Rate	Effect	\overline{P}_{F}	\overline{P}_{c}	K	Total/	Networks/	Total/	Networks/	Total/	Networks/
		L	C		arm	arm	arm	arm	arm	arm
					Mean pe	er network $= 4$	Mean pe	er network $= 3$	Mean pe	er network $= 2.5$
6%	33%	7.8%	11.6%	0.1	1671	418	1542	515	1478	592
				0.2	2057	515	1800	600	1671	669
				0.3	2442	611	2057	686	1864	746
6%	40%	7.1%	11.6%	0.1	1112	278	1026	343	983	394
				0.2	1368	343	1197	400	1112	445
				0.3	1625	407	1368	457	1240	496
8%	33%	10.4%	15.3%	0.1	1246	312	1150	384	1102	441
				0.2	1534	384	1342	448	1246	499
				0.3	1821	456	1534	512	1390	556
8%	40%	9.4%	15.3%	0.1	828	208	765	255	733	294
				0.2	1020	255	892	298	828	332
				0.3	1211	303	1020	340	924	370

 Table 1: Sample size requirements for two-arm group randomized network study

The sample size has been chosen to achieve 90% power to detect a 40% reduction in rate of infection, from 6% per year to 3.6% per year. This requires 445 networks per arm, followed for an average of 27 months (minimum of 18 month, maximum of 30 months), with a seroincidence evaluation of an average of 2.5 HIV-uninfected people per network (HIV-uninfected peer leader and one or more network members, HIV-uninfected at enrollment) and loss to follow-up of 10% per year, using two-sided alpha of 0.05 and intraclass correlation of 0.2. To achieve the same power to detect a 33% reduction, from 6% to 4%, requires 669 networks per arm.

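### The last row of Table 4 prints 80% power bounds (0.118 and 0.338) that cannot belong to its own inputs (Philadelphia control 0.250, null 0.125)

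*Protocol*

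**What the plan says.** Section 7.3.3 describes a two-stage analysis of behavioral correlates. The second stage tests whether the intervention changes behavior equally at both sites: "The null hypothesis states that the relative behavior change at each site is the same". On the method, the section says only "Power computations are based on use of generalized linear models for binomial data". The sample is fixed at "445 networks of average size 2.9 per arm, and it is assumed 2/3 of the networks are in Thailand".

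Table 4 gives, for nine scenarios, the control prevalence in Thailand (p00) and Philadelphia (p01), the intervention prevalence in Thailand (p10), the null value for the Philadelphia intervention arm (p11), and a lower and an upper bound. The text explains a bound as a true Philadelphia value at which "there would be 80% probability of detecting it was not the same behavior reduction as seen in Thailand".

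The last row (higher Philadelphia prevalence) reads, from p00 to the upper bound: "0.2 0.250 0.10 0.125 0.118 0.338". The sentence after the table, "The alternatives that there is reasonable power to detect seem useful; that is, they represent clinically relevant differences", makes no exception for it.

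**The concern.** A lower bound of 0.118 lies 0.7 percentage points below the null of 0.125. An upper bound of 0.338 lies above the Philadelphia control prevalence of 0.250. Read literally, the trial would have 80% power for a trivial difference in one direction, yet less than 80% power against a complete absence of effect in the other. No other row looks like this.

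The between-site comparison matters to the design. Section 2.3 relies on the behavioral mediators to argue that the intervention works in different settings. Section 7.3.2 says the primary outcome cannot be used to assess Philadelphia on its own. Table 4 is the power evidence for that comparison, and this row would mislead a reader about low-prevalence behaviors in Philadelphia.

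**Working it through.** **Inputs.** From Table 4: all nine rows. From Section 7.3.3: 445 networks of 2.9 per arm, two thirds in Thailand. So 445 × 2.9 = 1290.5 participants per arm, about 860 in Thailand and 430 in Philadelphia. Assumed: two-sided alpha 0.05, which Section 7.3.1 states for the primary endpoint ("using two-sided alpha of 0.05 and intraclass correlation of 0.2"); Section 7.3.3 gives no alpha.

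**Step 1: the null.** Equal relative change gives p11 = p01 × p10/p00 = 0.250 × 0.10/0.20 = 0.125. The printed null is reproduced.

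**Step 2: symmetry of the bounds.** For each row: down = ln(null/lower), up = ln(upper/null), centre = √(lower × upper). Rows 5 and 8 use the unrounded nulls 0.1875 and 0.3125.

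| Row | p01 | Null | Bounds | Down | Up | Centre/null | Upper/p01 |
|---|---|---|---|---|---|---|---|
| 1 | 0.800 | 0.400 | 0.258, 0.619 | 0.439 | 0.437 | 0.999 | 0.77 |
| 2 | 0.500 | 0.250 | 0.156, 0.401 | 0.472 | 0.473 | 1.000 | 0.80 |
| 3 | 0.200 | 0.100 | 0.056, 0.178 | 0.580 | 0.577 | 0.998 | 0.89 |
| 4 | 0.600 | 0.300 | 0.191, 0.471 | 0.452 | 0.451 | 1.000 | 0.79 |
| 5 | 0.375 | 0.188 | 0.115, 0.307 | 0.489 | 0.493 | 1.002 | 0.82 |
| 6 | 0.150 | 0.075 | 0.041, 0.136 | 0.604 | 0.595 | 0.996 | 0.91 |
| 7 | 0.850 | 0.425 | 0.275, 0.656 | 0.435 | 0.434 | 0.999 | 0.77 |
| 8 | 0.625 | 0.312 | 0.197, 0.496 | 0.461 | 0.462 | 1.000 | 0.79 |
| 9 | 0.250 | 0.125 | 0.118, 0.338 | **0.058** | **0.995** | **1.60** | **1.35** |

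The row 9 centre is √(0.118 × 0.338) = 0.1997. This step needs no assumption about link, alpha or clustering.

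**Step 3: what the table's own pattern gives for row 9.** Fitting the squared log half-width in rows 1 to 8 as a constant plus terms in 1/p00 and 1/p01 reproduces those half-widths to within 1.5%. For p00 = 0.2 and p01 = 0.25 the predicted half-width is 0.560:
- lower = 0.125 × exp(−0.560) = 0.071
- upper = 0.125 × exp(0.560) = 0.219

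A log-log fit gives the same values to three decimals.

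**Step 4: direct calculation.** For a log-link interaction test, Var = Σ(1−p)/(np) over the four cells. At the null this is (4 + 9)/860.3 + (3 + 7)/430.2 = 0.0384, so SE = 0.196. The bounds are 0.125 × exp(±2.802 × 0.196) = 0.072 and 0.216. With a design effect of 1 + (2.9 − 1) × 0.2 = 1.38 they are 0.066 and 0.238. With the variance taken at the alternative they are 0.064 and 0.205, or 0.055 and 0.222 with the design effect.

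**Step 5: power at the printed values** (log link, variance at the alternative).
- At 0.118: |ln(0.118/0.125)| = 0.058 and SE = 0.199, so the ratio is 0.29 and two-sided power is about 6%.
- At 0.25: ln 2 = 0.693 and SE = 0.170, so the ratio is 4.07 and power is 98%. With the design effect, SE = 0.200 and power is 93%. The SE implied by the other rows (0.560/2.802 = 0.200) also gives 93%.
- At 0.338: power exceeds 99.9% with or without the design effect.

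**Step 6: limit of the direct calculation.** It does not reproduce the rest of the table. The row 1 half-width comes out at 0.219 against 0.438 printed. For row 6 it is 0.669 against 0.600, so the discrepancy changes sign. Row 3 is close (0.055 and 0.182 against 0.056 and 0.178).

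**The case against.** The strongest case against giving this weight is that the row decides nothing. Section 7.3.3 takes the sample size as fixed by the primary endpoint, the analysis is secondary, and it is planned only if the primary result is positive. The same section warns that its power figures cover a single dichotomous outcome per participant and that repeated measures may overpower the test. The closing judgment on detectable differences fits eight rows and would fit a corrected ninth. All of this stands, and it limits the importance of the error without removing it.

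A reader might also infer more than the documents support:
- **That the row says the trial could not detect zero effect in Philadelphia.** The bounds mark 80% power. A value inside them has less than 80%, which is not inability to detect.
- **That the bounds were computed for a Philadelphia control prevalence of 0.40 and a null of 0.20.** The numbers fit: the Step 3 pattern gives 0.117 to 0.118 and 0.339 to 0.341. But 0.40 appears nowhere as a Philadelphia control prevalence, so this origin is conjecture. The printed 0.250 is 1.25 × the Thai 0.2, the same ratio as in the row above (0.625 = 1.25 × 0.5). The bounds are therefore likelier to be wrong than the inputs.
- **That 0.07 and 0.22 are the exact correct values.** They extend the table's pattern. With link and clustering allowance unstated, direct calculations run from 0.055 to 0.072 and from 0.205 to 0.238.

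A text-extraction fault is unlikely: every column is present and in order.

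**Conclusion.** The point holds as an error in one row: bounds of 0.118 and 0.338 cannot be 80% power bounds for a null of 0.125. Both are wrong. The lower claims 80% power where it is about 6%, and the upper implies less than 80% power against no effect where it is about 93% to 98%.

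The inconsistency rests on the table's internal pattern alone. The power figures also assume two-sided alpha 0.05, a log-link test, and either no clustering or a design effect of 1.38. The replacement values are approximate.

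The consequence is confined to the secondary site-interaction analysis. The primary sample size and primary analysis are unaffected, and the general conclusion drawn from Table 4 survives once the row is corrected.

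**What to change.** Recompute the last row of Table 4 for p00 = 0.2, p01 = 0.250, p10 = 0.10 and null 0.125, using the method that produced the other eight rows. Values of approximately 0.07 and 0.22 are expected. If the sponsor's records show that another Philadelphia scenario was intended, p01 and the null should be corrected instead so that inputs and bounds agree.

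State with the table the link function, the alpha level and any allowance for clustering within networks, so that every row can be reproduced. The cost is one recalculated row and one added sentence, with no change to design, sample size or conduct.
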